#### 4.9 OTHER ENDPOINTS

The following variables will be analysed as for continuous outcomes as specified above:

- CD4 (cells/mm^3), CD4:CD8 ratio
- Quality of Life: summary score

In addition, the following will be presented over scheduled visits:

- Suppressed HIV-RNA: number (%)
- QTc interval  $\leq$ 440ms: number (%)
- eGFR $<$ 60 ml/min/1.73m^2: number (%)
- Platelet count  $\geq$ 150x10^9/L: number (%)
- Low haemoglobin (Hb $\geq$ 12g/dL for males,  $\geq$ 11g/dL for females): number (%)
- ALT  $<$ 5xULN
- Merck p24 assay: To be specified.

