### 3 ANALYSIS PRINCIPLES

- The trial will be primarily analysed as intention-to-treat including all randomised participants. Based on the consideration that the trial is evaluating the efficacy, as measured by the impact on total CD4+ HV DNA of a novel intervention, sensitivity analyses will also be performed for immunological/virological outcomes excluding participants with incomplete intervention (temporary/complete stop of ART, vaccination, or vorinostat).
- Randomisation arms will be compared using data between baseline and the post-randomisation week 18 visit (inclusive). Data collected in the period between enrolment and randomisation will be reported for stratum I as baseline data.
- For continuous variables, the following will be presented by scheduled visits and by randomised group:
  - number of participants with a measurement
  - mean (SD) or median (IQR) of absolute values and of changes in absolute values from baseline
  - mean changes (plus point-wise 95% CI) from baseline in each randomised group, calculated using normal regression of absolute values, adjusting for the baseline measurement.
  - normal generalized linear regression models (using GEE) will be used for a global test of difference between treatment groups across all visits

If positively skewed, data will be log-transformed before the analysis. If parametric models/tests do not seem to be appropriate, rank tests will be performed.

- Binary and categorical variables will be tabulated, overall and by randomised group. Differences between groups at particular time-points will be tested using chi-squared tests (or exact tests if appropriate), and logistic regression models for adjusted analyses. GEE models will be used for a global test of difference between treatment groups across all visits.
- Time-to-event outcomes will consider time from baseline to the event date, using Kaplan-Meier estimation. For participants who have not reached the event in question, the date of last clinic visit will be used as a censoring time. Differences between groups in time-to-event outcomes will be tested using a log-rank test and Cox proportional hazard regression models (stratified by the stratification factors).
- Primary analyses will be adjusted for membership of stratum I versus stratum II; secondary analysis will be conducted without adjustment.

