### 4.3 PATIENT CHARACTERISTICS

The following baseline characteristics will be presented overall and by randomised group. For the grouping of quantitative variables, categories will be chosen after univariate inspection of the data, ensuring that a reasonable number of participants are represented in each category.

Before completion of randomisation, the same characteristics will also be reported for all patients enrolled but not by randomised group.

- Stratum: number (%) stratum I, stratum II
- Age: median (IQR), range; distribution in categories
- Sex: number (%) male, female
- Ethnicity: number (%) White, South Asian, South East Asian, Hispanic/Latino, Black African, Black Caribbean/American, mixed ethnic group, other
- Mode of HIV infection: number (%) sex between men, sex between men and women, injection drug use, blood products, unknown, other
- CD4 count (current): median (IQR), range; distribution into categories
- HIV-RNA: number (%) undetectable; distribution into categories
- Criteria for PHI diagnosis: number (%) positive HIV-1 serology, positive p24, HIV RNA or proviral DNA, 4th generation HIV test, western blot, RITA only.
- eGFR: median (IQR), range
- QTc interval: median (IQR), range
- Haematology/biochemistry/electrolytes/glucose/lipids/urine analysis: median (IQR), range of test results

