For each marker, the magnitude of a response is defined as the number of positive cells as percentage of their parental populations, after subtracting the negative control. For technical reasons, HIV antigens will be divided in non-overlapping pools values for each sample; responses will be added up for each marker.

At each time-point, the magnitude of responses, and the change from baseline will be analysed as for continuous outcomes as specified above.

- **CD8+ T cell antiviral activity (viral inhibition)**

Measurements using a flow cytometer-based assay [2] at enrolment (in recently infected patients), baseline, PR week 09-2, PR week 12-2, and PR week 16.

CD8+ T cell antiviral suppressive activity will be expressed as percentage inhibition and determined as follows:  $\frac{[(\text{fraction of p24} + \text{cells in CD4} + \text{T cells cultured alone}) - (\text{fraction of p24} + \text{in CD4+ T cells cultured with CD8+ cells})]}{(\text{fraction of p24} + \text{cells in CD4} + \text{T cells cultured alone})} \times 100$ .

CD8+ T cell antiviral suppressive activity will be analysed as described above for continuous outcomes.

- **Inflammatory biomarkers:**

For example CD4:8 ratio, immune exhaustion/activation markers, IL-6 and d-dimer, neuro-inflammation markers. Analysed as for continuous outcomes as specified above.

- **HIV cell associated RNA (arm B only):**

Measurements (copies/million 18S copies) pre and 2 hours post vorinostat at visits PR week 08-3, PR week 09-2, and PR week 12-2. Comparison of pre and post vorinostat values will be performed using paired t-tests (or paired rank-tests if appropriate).

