#### 4.8 SECONDARY ENDPOINTS: SAFETY

Adverse events pre-randomisation will be presented overall. Adverse events post-randomisation will be presented by randomised arm. For all adverse event types, the total number of events, the number of participants with at least one event, and the maximum grade per participant will be given. Analysis of adverse event outcomes will be based on the number ever experienced a type of adverse event which will be compared as for binary outcomes. Timing of events, and recurrent events will also be described.

Where relevant and established, events will also be presented by severity grade, and by relationship to study treatment (definitely, probable, possible, unlikely, unrelated).

The following adverse event outcomes will be analysed:

- Grade 3 or 4 adverse events
- Notable events
- Treatment-modifying adverse events (any grade)
- Post-vaccination solicited events (arm B only; any grade):
  - solicited local injection site reactions: pain, itching, redness/blistering
  - solicited general reactions: fever, muscle aches, generalised itching, joint aches, headache, nausea, general discomfort
- SAEs, overall and by type of SAE (fatal, life-threatening, hospitalisation, disability, other).
- Lab abnormalities.
- Tabulation of adverse events of all grades

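### SAP 4.9 lists post-baseline QTc, eGFR, platelets, haemoglobin and ALT only against the entry limits and does not explicitly plan a by-arm estimate of change

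*SAP*

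**What the plan says.** SAP 4.9 has two lists. The first opens "The following variables will be analysed as for continuous outcomes as specified above" and holds CD4, CD4:CD8 ratio and the quality-of-life score. The second opens "In addition, the following will be presented over scheduled visits". It holds suppressed HIV RNA, "QTc interval $\leq$ 440ms: number" (%), eGFR below 60, platelets at or above 150, a haemoglobin row, ALT below 5 times the upper limit, and an assay still to be specified. This list does not mention arm, change from baseline or the continuous method. The ALT row names no statistic, and the row labelled as low haemoglobin gives the limits for normal haemoglobin.

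SAP 3 sets general rules. One begins "For continuous variables, the following will be presented by scheduled visits and by randomised group" and includes "mean changes (plus point-wise 95% CI) from baseline in each randomised group", from a regression adjusted for baseline. Another has binary variables tabulated by arm, with tests at time-points and a GEE test across visits. Neither rule lists its variables.

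SAP 4.3 summarises baseline values on the measured scale, for example "QTc interval: median (IQR), range". SAP 4.8 compares adverse events, including laboratory abnormalities, by the "number ever experienced a type of adverse event which will be compared as for binary outcomes".

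**The concern.** The SAP 4.9 cut-offs for QTc, platelets, eGFR, haemoglobin and ALT are the randomisation limits in Protocol 3.3.3 (with equivalents for Cohort II in 3.4.1 and 3.4.2) and the limits for starting vorinostat in Protocol 5.5. A participant can move a long way inside a limit without changing category. Near-equal counts in the two arms would then say little, yet could be read as showing no effect.

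The protocol itself gives reasons to look at these variables. Section 5.14.3 names low platelets among the commonest effects of vorinostat. Section 1.1.1.C describes dose-related anaemia and thrombocytopenia, and 1.1.1.D reports creatinine rises in 41 of 87 lymphoma patients. QTc is a condition for starting the drug. In Table 1 the ECG and routine blood rows are not restricted to Arm B, so a randomised comparison of measured values is available from data already collected. (Table 2, for Cohort II, could not be read in the text reviewed and is assumed to match.) At stake is how informative the supportive safety report will be. The primary and efficacy analyses are unaffected.

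**Working it through.** **Reading the sections together.** If the SAP 3 continuous rule applied automatically to every measured variable, the first list in 4.9 would not be needed. SAP 4.7 also invokes the rule endpoint by endpoint ("analysed as for continuous outcomes as specified above"): integrated DNA, T-cell responses, viral inhibition and biomarkers each carry it. QTc, eGFR and the laboratory values get a measured-scale summary at baseline in 4.3 and a cut-off afterwards in 4.9. This suggests, without proving, that the cut-off is the intended post-baseline method.

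**Plan's own figure.** The plan gives no figure for these variables. Its only design figure is 94% power with 52 participants for the primary endpoint (86% for a 45% reduction). With residual SD 0.4 × √((1 + 0.7)/2 − 0.5²) = 0.3098 and 26 per arm, the power is 93.9% and 85.6%, so both figures reproduce. Only the 26 per arm is carried forward.

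**One cell worked by hand (all inputs assumed).** Take a control QTc mean of 410 ms, SD 20, correlation with baseline 0.5 and a true shift of 15 ms.
- Proportion above 440 ms: control 1 − Φ(30/20) = 0.067; Arm B 1 − Φ(15/20) = 0.227. Fisher's exact test has 24% power.
- Regression: residual SD 20 × √0.75 = 17.32; SE 17.32 × √(2/26) = 4.80; 15/4.80 = 3.12; Φ(3.12 − 1.96) gives 88% power.

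Over means of 400 to 420 ms and SDs of 15 to 25 ms, the same 15 ms shift gives about 0% to 57% for the count and 71% to 99% for regression.

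**Simulation that respects the entry limit (all inputs assumed).** Baseline QTc mean 395 to 415 ms, SD 20, truncated at 440; SD of change 12 to 20 ms; one post-baseline visit; 4,000 replicates per cell. The two graded counts use the scale in Protocol 1.1.1.B and suppose that every qualifying rise is reported.

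| True shift | Count >440 ms | Grade ≥2 count | Any-rise (Grade ≥1) count | Baseline-adjusted regression |
|---|---|---|---|---|
| +5 ms | 0–4% | 0–2% | 7–15% | 14–31% |
| +10 ms | 0.3–12% | 0–8% | 21–55% | 41–84% |
| +15 ms | 2–32% | 4–25% | 44–84% | 74–99% |

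With no shift, regression rejects in 4.7% to 5.4% of replicates. Its 95% CI half-width is about 2.01 × SD of change × √(2/26): 6.7 ms at SD 12 and 11.2 ms at SD 20, whatever the true shift.

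**More than one visit.** With two on-drug visits, any-visit counts and an assumed correlation of 0.5 between changes, power at +15 ms is 7% to 40% for the >440 ms count and 24% to 40% for the Grade ≥2 count. Single-visit regression still has more (74% to 99%).

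**Platelets (all inputs assumed).** Geometric mean 220 to 250, log SD 0.22 truncated at 150, SD of log change 0.14 to 0.20. For a 10% fall, the count below 150 has 0.2% to 5% power against 46% to 77% for regression. For a 15% fall the figures are 1% to 15% against 82% to 98%. Platelet grade limits are in Appendix III, which was not available, so a graded comparison could not be computed.

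**The case against.** The strongest reply is that SAP 3 already answers the question. Its continuous rule is unqualified, these are continuous measurements, and the words opening the second list in 4.9 can mean that threshold tables come on top of the general presentation. Restating a rule for some endpoints does not switch it off for others. That reading is tenable, so the documents do not support inferring that no by-arm change analysis exists. What stands is that the plan does not say which reading applies.

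Second, by-arm comparisons do exist. The SAP 3 binary rule supplies arm-level tables, tests and GEE for the threshold counts. SAP 2.3 collects all grades after randomisation and 4.8 reports them by arm with maximum grade. The QTc scale in Protocol 1.1.1.B also grades rises over baseline. A Grade 3 rise would stop vorinostat under Table 5 and count as treatment-modifying. These are real safeguards. A reader might infer that a dangerous QTc rise could pass unseen, but the documents do not support that. In the simulation, the expected number of Arm B participants with a rise of 60 ms or more who stay at or below 440 ms is at most 0.05 of 26. The limit of the safeguards is that event counts depend on sites calculating and reporting each rise, and they do not estimate an arm difference in measured values.

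Third, the thresholds have a purpose: they show who stays within the limits for starting vorinostat. That is a reason to keep them.

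Fourth, no document gives an SD or an expected shift. Protocol 1.1.1.B reports no significant QTc change in 25 volunteers after a single 800 mg dose, so the true shift may be small. This is correct, and the power contrast is not a measured deficiency. An interval is still informative when the true shift is near zero, whereas a threshold count is not.

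**Conclusion.** The point holds as a minor one about supportive safety. SAP 4.9 presents five measured safety variables by position against limits that every eligible participant meets at entry, and does not explicitly plan a by-arm estimate of change for them. SAP 3 and SAP 4.8 narrow the gap without closing it.

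The size can only be illustrated. Across both sets of assumed inputs, a 15 ms QTc shift at one visit gives roughly 0% to 57% power for the count above 440 ms and 71% to 99% for baseline-adjusted regression. The ordering is stable over these inputs, but the levels depend on them. The closest competitor is the any-rise count, which needs every small rise to be reported as an event. The figures do not show bias, an invalid inference or a missed harm, and should not be quoted as the trial's actual power for safety.

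**What to change.** In SAP 4.9, move QTc, eGFR, platelet count, haemoglobin and log ALT into the list analysed as continuous outcomes. Report change from baseline by visit and arm, and the baseline-adjusted arm difference with its 95% CI. The least that would do is one sentence stating that the SAP 3 continuous rule covers these variables.

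Keep the threshold counts, and state that they are tabulated by arm under the SAP 3 binary rule. In the same edit, correct the haemoglobin row so that label and limits agree, and name a statistic for ALT.

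Optional: tabulate the largest QTc increase by arm (<30, 30 to <60, ≥60 ms) from the recorded ECGs. Also optional: state ECG time relative to dose if it was recorded. With a half-life of about 2 hours (Protocol 1.1.1.A), a pre-dose ECG is close to off-drug.

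The cost is a few lines of SAP text and a few extra safety tables. No new data are needed and the primary analysis does not change.
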